10.6.2. Clinical Laboratory Assessments

Clinical laboratory assessments to be conducted in this study are shown in [Table 10](#). Blood and urine specimens will be analyzed at the CRU or its designated laboratory as appropriate. Clinical laboratory specimens are to be collected under fasting condition (subjects should not take food or fluids, except of water, for at least 6 hours prior to specimen collection).

The investigator or designee will perform an assessment of all clinical laboratory data for clinical significance. Clinical laboratory parameters will be determined for all subjects using the CRU's or designated laboratory's routine clinical laboratory methods. Laboratory test results that are abnormal and considered clinically significant must be reported as adverse events (Section 12.1.4).

Monitoring of Laboratory Abnormalities

In the event of unexplained or unexpected clinically significant laboratory test values, the investigator may choose to repeat the test(s) as soon as possible and follow until the results have returned to the normal range and/or an adequate explanation for the abnormality is found. The investigator will clearly mark all laboratory test values that are outside the normal range on the laboratory reports and will indicate which of these deviations are clinically significant. Any abnormal laboratory result judged by the investigator to be clinically significant will be classified as an adverse event and will be recorded on the adverse event eCRF. The investigator will also determine the severity and causality.

Table 10: Clinical Laboratory Assessments

Hematology
Leukocytes
Erythrocytes
Hemoglobin
Hematocrit
Platelets
Partial automated differential:
lymphocytes
monocytes
eosinophils

basophils
neutrophils
MCV
MCH
MCHC

Coagulation

PT
aPTT
PT INR

Clinical Chemistry

Total bilirubin
Direct bilirubin
Indirect bilirubin
Gamma-GT
AST
ALT
LDH
Creatinine
Urea
Total protein
Glucose
Inorganic phosphate
Sodium
Potassium
Calcium
Chloride
Albumin
Magnesium

Urinalysis

pH
Color
Appearance
Specific gravity
Glucose
Ketones
Protein
Blood
Standard microscopy:

Casts
Bacteria
RBCs
WBCs

Smoking Screen (Screening and Admission Only)

Cotinine

**Follicle-Stimulating Hormone (FSH) Test (Screening Only) for Female Subjects for
Gender Assessment Group^a**

FSH

Serology (Screening Only)

HBsAg
HIV Ag and Ab
HCV Ab

Drugs of Abuse / Alcohol Screen (Screening and Admission Only)

Amphetamine
Barbiturate
Benzodiazepine
Cocaine
Methadone
Opiates
Oxycodone
Phencyclidine
Propoxyphene
Cannabinoid (THC)
MDMA (Ecstasy)
Methaqualone
Ethanol (Alcohol) (Both urine and breath tests)
Tricyclic Antidepressant (TCA)

Other Assessments

Alpha-1-acid glycoprotein
Total cholesterol
LDL cholesterol
HDL cholesterol

^a Postmenopausal status for females of non-childbearing potential will be further confirmed with follicle-stimulating hormone (FSH) serum levels that are consistent with postmenopausal status. Refer to Inclusion Criteria for details (Section 8.1).

ALT: alkaline transaminase; aPTT: activated partial thromboplastin time; AST aspartate transaminase; Gamma-GT: glutamyl transpeptidase; FSH, follicle-stimulating hormone (FSH); HbsAg: hepatitis B surface

antigen; HCV Ab: hepatitis C antibody; HDL: high density lipoprotein; HIV Ab: human immunodeficiency virus antibody; LDH: Lactic dehydrogenase; LDL: low density lipoprotein; MCH: mean corpuscular hemoglobin; MCHC: mean corpuscular hemoglobin concentration; MCV: mean corpuscular volume; PT: prothrombin time; PT INR: PT international normalized ratio; RBC: red blood cell; TCA: tricyclic antidepressant ; THC: cannabinoid; WBC: white blood cell.

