3. LIST OF ABBREVIATIONS

Abbreviation	Term
5-HT	Serotonin 5-hydroxytryptamine
ADD	After-discharge durations
ADME	Absorption, distribution, metabolism, and excretion
AE	Adverse event
AEDs	Antiepileptic drugs
ALT	Alkaline transaminase
aPTT	Activated partial thromboplastin time
AST	Aspartate transaminase
AR	Accumulation ratio
AUC	Area under the concentration-time curve
AUC _{24hr}	Area under the concentration-time curve from time zero to 24 hours post-dose
AUC _∞	Area under the concentration-time curve from 0 to infinity
AUC _t	Area under the concentration-time curve from 0 to t
AUC _τ	Area under the concentration-time curve over the dosing interval
BA	Bioanalytical
BCRP	Breast cancer resistance protein
BK	Big Potassium
BLQ	Below the limit of quantitation
BMI	Body mass index
BSA	Body surface area
CHO	Chinese hamster ovary
CL	Total clearance
CL/F	Apparent clearance
CL _R	Renal clearance
C _{max}	Maximum concentration
CF	Cystic fibrosis
CFR	Code of Federal Regulations
CNS	Central nervous system
CPAP	Clinical pharmacology analysis plan
CRO	Contract research organization

Abbreviation	Term
CRF	Case report form
CRU	Clinical research unit
C-SSRS	Columbia-Suicide Severity Rating Scale
CSR	Case Study Report
CV	Coefficient of Variation
CYP	Cytochrome P450
DMCM	Methyl 6,7-dimethoxy-4-ethyl- β -carboline-3-carboxylate hydrochloride
ECG	Electrocardiogram
eCRF	Electronic case report form
ED ₅₀	Half-maximal effective dose
EDC	Electronic data capture
EDTA	Ethylenediaminetetraacetic acid
EEG	Electroencephalography
EMA	European Medicines Agency
EOS	End of Study
FDA	Food and Drug Administration
FSH	Follicle-stimulating hormone
FIH	First-in-human
f _e	Fraction of drug dose excreted in urine
F _{rel}	Relative bioavailability
FU	Follow-up
GABA	Gamma-aminobutyric acid
Gamma-GT	Glutamyl transpeptidase
GCP	Good Clinical Practice
GI	Gastrointestinal
GLP	Good Laboratory Practice
GMS	Generalized myoclonic seizures
GTCS	Generalized tonic-clonic seizures
HBsAg	Hepatitis B surface antigen
HCN	Hyperpolarization-activated cAMP-regulated cation
HCV	Hepatitis C virus

Abbreviation	Term
HCV Ab	Hepatitis C antibody
HDL	High density lipoprotein
HED	Human equivalent dose
HEK	Human embryonic kidney
hERG	Human ether-à-go-go related gene
HIPAA	Health Insurance Portability and Accountability Act of 1996
HIV Ab	Human immunodeficiency virus antibody
HIV Ag	Human immunodeficiency virus antigen
hNav	Human voltage-gated sodium channels
hDAT	Human dopamine transporter

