In vitro metabolism studies indicated that SKL24741 had high metabolic stability in rat, rabbit, dog, monkey and human microsomes, and moderate metabolic stability in mouse microsomes. In hepatocytes, SKL24741 showed high metabolic stability in rats and rabbits and moderate stability in mice, dogs, humans, and monkeys. In a separate hepatocyte assay, SKL24741 showed notably greater metabolism in monkeys, compared to other species. A total of six SKL24741 metabolites were found following incubation with mouse, rat, rabbit, dog, monkey, and human hepatocytes. Similar metabolic profiles were observed in hepatocytes from rats, rabbits, dogs, and humans, with no unique human metabolites. Metabolite M1 was not observed in monkey hepatocytes but was seen in human hepatocytes and all other species. SKL24741 showed low potential for covalent binding to liver proteins and low potential to form reactive metabolites that could bind to liver proteins. At a concentration up to 100 μ M, SKL24741 had no inhibitory effect on cytochrome P450 (CYP) 2B6, CYP2C8, CYP2D6, and CYP3A4 (i.e., $IC_{50} > 100 \mu$ M for isozymes). The IC_{50} values CYP1A2, CYP2C9, and CYP2C19 were 21.1 μ M, 99 μ M, and 58.7 μ M, respectively.

Excretion of SKL24741 was evaluated following single oral administration of [^{14}C]-SKL24741 in rats. The primary route of elimination of radioactivity was in the feces, with high levels being recovered in the bile of cannulated rats, suggesting that hepatic clearance and biliary excretion play an important role in the elimination of [^{14}C]-SKL24741.

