In a GLP 28-day repeat-dose study toxicity and TK study, male and female rats were administered 0, 15, 30, or 40 mg/kg/day SKL24741. No unscheduled mortalities were observed. Clinical observations were dose-responsive and included transient ataxia and hypoactivity for both sexes administered \geq 30 mg/kg/day and low body carriage for animals administered 40 mg/kg/day. Isolated incidences of hunched appearance and lateral recumbency were also observed at 40 mg/kg/day. Clinical signs were considered adverse at 40 mg/kg/day due to the nature and severity of the observations. Dose-dependent decrease in body weight, correlating with decreased food consumption, was observed at \geq 30 mg/kg/day; however, these observations were not considered adverse due to their transient nature and reversibility. Clinical chemistry changes included mild, reversible, higher cholesterol concentration in males and females administered \geq 15 mg/kg/day and \geq 30 mg/kg/day, respectively, which were not considered adverse. SKL24741-related increased liver weights were observed in males administered \geq 30 mg/kg/day and females administered \geq 15 mg/kg/day. Microscopic liver findings of minimal centrilobular hepatocyte hypertrophy were observed in males and females administered \geq 30 mg/kg/day. These findings were consistent with potential microsomal enzyme induction in the liver, an adaptive response, and were considered non-adverse due to their minimal severity and partial recovery following the 2-week recovery phase. Based on FDA recommendation, a NOAEL of 15 mg/kg/day was considered for calculating the starting dose (mean combined sex C_{max} values was 3.32 µg/mL and AUC_{24hr} 61.2 µg*h/mL).

In a non-GLP toxicity study, male and female dogs were administered a single dose of 20, 60, 100, or 300 mg/kg SKL24741. At doses \geq 100 mg/kg, clinical signs of lateral (only 300 mg/kg female) and sternal recumbency, ataxia, hypoactivity, emesis, and/or foamy white vomitus, and excessive salivation were observed. Decreased food consumption was noted in animals administered \geq 60 mg/kg with full recovery before the next dosing occasion. The MTD following single oral administration in dogs was 100 mg/kg.

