11.1. Sample Size and Power

No formal sample size calculations have been performed. This study utilizes the sample size, or the number of subjects, that is commonly employed in early clinical pharmacology studies, in order to achieve the study objectives. Subjects who do not complete all the treatments and assessments specified in this protocol may be replaced.

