11.4.1. General Considerations

The SK Life Science, Inc. Biometrics designated CRO will analyze the safety data derived from this study. Only descriptive analyses will be performed; no statistical hypothesis testing will be done. Continuous variables (e.g., age) and PK parameters will be summarized by means of descriptive statistics (e.g., number of subjects (n), arithmetic mean, arithmetic standard deviation (SD), standard error of the mean (SEM), coefficient of variation (CV), geometric mean, geometric CV, median, first and third quartiles, minimum, and maximum). If the measurements in the source (raw) data are integers, then the corresponding mean and median will be presented to 1 decimal place and the SD to 2 decimal places; if the measurements are obtained to 1 decimal place, then the mean and median will be presented to 2 decimal places and the SD to 3 decimal places; and so forth. Minimum and maximum will be displayed as reported in the source (raw) data. Categorical variables (e.g., presence of an adverse event) will be summarized using counts and percentages. Percentages will be presented to 1 decimal place unless otherwise specified. Statistical analysis results will be presented by treatment group and as appropriate.

All subject data, including derived, will be presented in the subject data listings; listings will display all subjects who were randomized and/or dosed with the study drug.

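### Table 10 omits alkaline phosphatase, so the ALT-to-alkaline-phosphatase ratio cannot be calculated from any scheduled draw; gamma-GT and fractionated bilirubin compensate only in part

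*Protocol*

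**What the plan says.** Section 10.6.2 of the protocol fixes the panel: "Clinical laboratory assessments to be conducted in this study are shown in" Table 10. The liver-related tests in its Clinical Chemistry block are total, direct and indirect bilirubin, gamma-GT, AST, ALT and LDH. No reflex or add-on test is named. The same section lets the investigator repeat unexplained, clinically significant tests and follow them until they are normal or explained.

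The Table 10 footnote gives "ALT: alkaline transaminase; aPTT: activated partial thromboplastin time; AST aspartate transaminase; Gamma-GT: glutamyl transpeptidase". Section 3 (List of Abbreviations) also expands ALT as "Alkaline transaminase".

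Two nonclinical sections bear on the liver:

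- Section 4.1.1.3 reports that liver weights rose in the 28-day rat study, in females from 15 mg/kg/day and in males from 30 mg/kg/day. Centrilobular hypertrophy of minimal grade was seen in both sexes from 30 mg/kg/day. The protocol's reading is: "These findings were consistent with potential microsomal enzyme induction in the liver, an adaptive response". It classes the findings as non-adverse.
- Section 4.1.1.2 reports a radiolabel excretion study in rats, with high recovery in bile, "suggesting that hepatic clearance and biliary excretion play an important role in the elimination of" the labelled drug.

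**The concern.** This is a first-in-human study, and laboratory safety is part of its primary endpoint (Section 6.1). If ALT rises, a reader of the data will want to know whether the pattern is mainly hepatocellular or mainly cholestatic. The standard summary is ALT divided by alkaline phosphatase, each as a multiple of its upper limit of normal. Half of that ratio is never measured.

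A statistical analysis plan cannot repair this, because it can only summarize analytes that are collected. Section 11.4.4 sets the safety profile against placebo, and Section 11.4.4.2 summarizes laboratory values as changes and shifts from baseline. An alkaline phosphatase value obtained only after a signal fits neither comparison.

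**Working it through.** The plan states no figure to reproduce. "No formal sample size calculations have been performed" (Section 11.1) and "Only descriptive analyses will be performed; no statistical hypothesis testing will be done" (Section 11.4.1), so power and error rates do not enter. The check is a count and a comparison of sections.

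**1. Count of the chemistry block in Table 10.**
- Liver-related: three bilirubin fractions, gamma-GT, AST, ALT, LDH = 7.
- Other: creatinine, urea, total protein, glucose, inorganic phosphate, sodium, potassium, calcium, chloride, albumin, magnesium = 11.
- 7 + 11 = 18 analytes, none of them alkaline phosphatase. It is also absent from the Other Assessments block and from the rest of the protocol.

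**2. Reach of the omission.** Planned subjects: 60 + 6 in Part A and 32 in Part B, 66 + 32 = 98. Table 1 marks five chemistry draws in Part A (Screening, Day -1, Day 2, Day 4, Follow-up). The Part B row of Table 2 carries seven marks. None of these draws would give an alkaline phosphatase value.

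**3. What the missing value does to the ratio.** Let R = (ALT ÷ its upper limit) / (alkaline phosphatase ÷ its upper limit). The inputs below are assumed, since the protocol gives none: ALT at 5 times and gamma-GT at 3 times their limits.

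| Alkaline phosphatase (assumed) | R |
|---|---|
| 1 × limit | 5 / 1 = 5.0 |
| 3 × limit | 5 / 3 = 1.7 |

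R differs threefold while the ALT and gamma-GT values on file are the same. Bilirubin fractions could still differ between the two cases, so the collected data need not be identical throughout.

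**4. Could the value come by another route?** Section 10.6.2 allows tests to be repeated, and Section 12.1.4 foresees that a result may call for further diagnostic testing. Both apply only once an abnormality has appeared, and neither names alkaline phosphatase. A subject tested in this way would have no Screening or Day -1 value. The planned placebo subjects (10 cohorts × 2 + 4 cohorts × 2 = 28, from Table 4) would have no scheduled values for comparison.

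**5. Relevance to this compound.** The 28-day rat study used 0, 15, 30 and 40 mg/kg/day, so female liver weights rose at the lowest active dose. Section 4.2.2 makes exposure at 15 mg/kg/day in rats (Cmax 3.32 µg/mL, AUC 61.2 µg·h/mL) the ceiling for human exposure. The trial may therefore approach the exposure at which the rat change was seen.

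**6. Expansion of ALT.** It is wrong in both places where it is given (Section 3 and the Table 10 footnote).

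**The case against.** The strongest reply is that the panel is not blind to liver injury, and that is correct. Several stronger readings suggest themselves, and the documents do not support them.

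- *A liver signal could not be classified at all.* ALT, AST, LDH, gamma-GT and three bilirubin fractions, including "Direct bilirubin", are collected. A hepatocellular rise would be visible, and cholestasis could be judged in part. What is lost is the ratio.
- *Gamma-GT is useless here because enzyme induction raises it.* The protocol mentions potential induction but never links it to gamma-GT, so the point does not rest on this.
- *The nonclinical data already show liver injury.* The protocol calls the rat findings adaptive and non-adverse, with partial recovery. Excretion of radiolabel in bile is not evidence of cholestasis. In the 7-day dog study, liver is one of 13 organs listed with weight changes and no direction is given. The account of the 28-day dog study reports no liver finding.
- *The stopping rule is impaired.* The rule in Section 7.3 turns on the number of subjects, severity and relatedness, not on the pattern of liver injury.
- *The value could never be recovered because no serum is kept.* The protocol does not say whether chemistry specimens are retained.
- *The misnaming of ALT caused the gap.* Table 10 lists ALT itself, and Section 12.1.4 uses ALT in its ordinary sense. The expansion is a clerical error, although the sponsor might confirm that alkaline phosphatase was not dropped by mistake.

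It also stands that the protocol does not commit to classifying liver signals by pattern, so no planned analysis is contradicted. What remains is a routine comparator missing from a fixed panel, which later discretionary testing cannot supply with a baseline or placebo values.

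**Conclusion.** The point holds as a limited design gap of low to moderate importance. The ratio would be unavailable for all 98 planned subjects at every scheduled draw, and the remaining liver tests offset this only in part. The practical effect depends on a liver signal occurring, and the documents give no basis for putting a probability on that. The conclusion assumes that Table 10 is the full list of what the laboratory will report, as Section 10.6.2 states. The change is worth making mainly because it is cheap and cannot be left to the analysis stage. The ALT expansion is a separate editorial error with no bearing on the data.

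**What to change.** Add alkaline phosphatase to the Clinical Chemistry block of Table 10 at every existing chemistry draw in Parts A and B, and summarize it with the other liver tests under Section 11.4.4.2. The cost is one routine analyte on blood already drawn, with no extra draw, visit or staff. The downside is a few more laboratory values to review.

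Separately, correct the expansion of ALT to alanine transaminase in Section 3 and in the Table 10 footnote.

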10.6.3. Physical Examinations and Vital Signs

A full physical examination (review of all body systems), an abbreviated (symptom-directed) physical examination, and vital sign evaluation will be performed at select study visits, as specified in [Table 1](#) and [Table 2](#).

A full physical examination includes a review of the following systems: head/neck/thyroid, eyes/ears/nose/throat, respiratory, cardiovascular, lymph nodes, abdomen, skin, musculoskeletal, and neurological. Breast, anorectal, and genital examinations will be performed when medically indicated. For the conduct of the eye examination, the site's standard procedures should be followed.

Physical examinations are to be performed by the Principal Investigator or designee (physician, physician assistant, or nurse practitioner) listed on the Form FDA 1572.

Vital sign evaluations include blood pressure (systolic and diastolic measurements in supine and standing in the same sequence in each subject, in order to allow orthostatic measurements), temperature, heart rate, respiratory rate, and arterial oxygen saturation (SaO₂) (using pulse oximetry). Additional vital sign assessments may be performed if clinically indicated, in the opinion of the investigator. Clinically significant abnormal findings in vital signs and physical examination will be reported as adverse events.

10.6.4. Electrocardiograms

For study conduct, electrocardiograms (ECGs) will be classified as either safety or triplicate ECGs at the time points indicated in [Table 1](#) and [Table 2](#). Electrocardiograms will be recorded using the site's standard ECG equipment. All ECGs will be obtained using instruments that analyze data using the same algorithms and produce the same data for interpretation. Digital ECGs will be captured and transferred to the designated core cardiology laboratory for ECG analysis. Collection of additional ECGs for routine safety monitoring at additional time points or days is at the discretion of the investigator based on GCP.

ECGs will be obtained using a Mortara continuous 12-lead digital ECG recorder. The ECG will include all 12-standard leads and will be recorded at a paper speed of 25 mm/sec. Standard ECG parameters will be measured, including heart rate (HR), RR, PR, QT, QTc intervals, and QRS duration. All ECGs should be collected after at least 5 minutes of supine rest and prior to blood sample collection. The device will remain connected to the subject during the collection periods as appropriate. The ECG data will be transmitted wirelessly to the Surveyor system, which will extract ECG recordings at the protocol specified time points.

Triplicate ECGs will be extracted approximately 1 minute apart reviewed and analyzed by the central ECG laboratory. The ECG extractions will be time-matched to the PK samples but obtained before the actual sampling time to avoid changes in autonomic tone associated

with the psychological aspects of blood collection as well as the reduction in blood volume subsequent to blood collection. The continuous ECG data will be sent to the central ECG laboratory for a high-resolution measurement of the cardiac intervals and morphological assessment. The ECG core laboratory staff will be blinded to treatment, time, and study day identifiers.

10.6.4.1. Safety 12-Lead ECGs

Standard 12-lead ECGs should be performed at the time points indicated in [Table 1](#) and [Table 2](#), in addition to any other times, if clinically indicated. The following guidelines must be followed:

- The subject will be instructed to rest in the supine position for at least 5 minutes before having an ECG performed,
- The ECG will be performed prior to any other procedures that may affect heart rate (e.g., blood draws).

The ECG data traces will be made for safety review by the investigator and maintained with source documentation. Any clinically significant ECG abnormalities at screening will exclude the subject's participation in the study. Thereafter, clinically significant abnormal findings will be reported as adverse events.

To ensure safety of the subjects, the Principal Investigator or designee will make comparisons to Day -1 (baseline) measurements. If the QTc is increased by >60 msec from the Day 1 pre-dose value or an absolute QTc value is >500 msec for any scheduled ECG, 2 additional ECGs will be collected, approximately 2 to 4 minutes apart, to confirm the original measurement. If either of the QTc values from these repeated ECGs remain above the threshold value (>60 msec increase from the Day 1 pre-dose; or is >500 msec), a single ECGs must be repeated at least hourly until QTc values from 2 successive ECGs fall below the threshold value that triggered the repeat measurement.

